6.3 MEASURES TO MINIMIZE BIAS: RANDOMIZATION AND BLINDING

Randomization Procedures

A web-based central randomization system will be developed by the DCC and installed on the WebDCU[™] HOBIT study website. The objective of randomization is to prevent possible selection bias by providing random treatment assignment to each subject, and to prevent accidental treatment imbalances for the known prognostic variables. Balancing of prognostic variables will be conducted using the Minimal Sufficient Balance randomization algorithm which aims to maximize the treatment allocation randomness while containing the baseline covariate imbalances within a pre-specified limit. The randomization scheme will be fixed allocation balanced across pre-specified covariates during a burn-in period (first 56 randomizations; 11 in control and 6 in each active arm except arm 2.5 ATA+NBH which is 9 subjects). Imbalances in the following baseline covariates between the treatment groups will be controlled: age, Baseline GCS score, and enrolling site. Once 56 subjects are randomized (in order to accrue outcome information in each arm), response-adaptive randomization (RAR) will be utilized for a maximum of 200 subjects with the goal of maximizing the likelihood of identifying the most effective treatment arm with regards to the GOS-E response. The allocation probabilities will be proportional to the probability that the arm is the best. The target allocation ratio will be updated after

every 20 subjects enrolled (note: the last interim analysis will be at 176 subjects before the final analysis at 200 subjects) . To ensure proper randomization, the unblinded statistical programmer will have access to the randomization information in order to oversee the quality control of the computer program. Randomization will occur via the study-specific password-protected website accessed by an authorized research coordinator or investigator at the clinical site. If, in rare circumstances, the web system is not available, the coordinator or investigator will have access to emergency randomization procedures that will allow the site to randomize the subject. Upon randomization by the authorized person at each center, an e-mail notification will be sent to the Study EC, Site PI, Site Primary Study Coordinator and relevant SIREN CCC and DCC personnel. Subjects will be considered enrolled in this trial at the time of randomization, regardless of whether or not they start or complete study treatment. The entire randomization process will be blind to all study team members.

Blinding

Following serious consideration of sham HBO treatments for the control group, the decision was made not to proceed with blinding for the following reasons. 1) It is impossible to perfectly blind a sham HBO treatment (Weaver 2002, Clarke 2009). The HBO technician administering the HBO and managing the chamber will be obviously aware of the treatment administered. In the case of a multiplace chamber, it will be completely obvious to the critical care hyperbaric nurse and any other personnel in attendance in the chamber whether there is a pressure being applied. In addition, even in the case of a monoplace chamber where brain tissue O2 monitoring is carried out, the treatment applied will be obvious. If for any reason blood gases have to be performed, treatment will be obvious. There are other management situations where it will be required by the treatment team to know whether or not the subject is under pressure. 2) Evaluation of any potential harm from HBO treatment should include the potential increased morbidity associated with transporting subjects to an HBO chamber (see adverse event section). Any outcome difference resulting from transportation of critically ill subjects should be accounted for in the HBO group only. 3) Primary outcome assessments will be done by blinded evaluators who were not involved in the treatment portion of the subject's course.

6.4 STUDY INTERVENTION COMPLIANCE

Adherence to the study protocol will be assessed and verified based on a review of hyperbaric oxygen treatment logs. These logs will document key data points including: start time for HBO treatment, end time for HBO treatment, start time for NBH treatment, end time for NBH treatment, compression time, and decompression time. Completion of these logs will be mandatory.

7 STUDY INTERVENTION DISCONTINUATION AND PARTICIPANT DISCONTINUATION/WITHDRAWAL

7.1 DISCONTINUATION OF STUDY INTERVENTION

- 1. Cardiac arrest or serious arrhythmias
- 2. Spontaneous pneumothorax
- 3. Seizure
- 4. Unstable vital signs, BP, arrhythmias
- 5. Refractory intracranial hypertension
- 6. Refractory low CPP
- 7. Increasingly high peak inspiratory airway pressures
- 8. Uncontrolled bleeding
- 9. Inability to ventilate

7.2 PARTICIPANT DISCONTINUATION/WITHDRAWAL FROM THE STUDY

- 1. Regardless of whether a subject was initially enrolled with informed consent or EFIC, an LAR may withdraw the subject from further participation at any time and for any reason.
- 2. Participants and their LARs are free to withdraw from participation in the study at any time upon request.
- The reason for participant discontinuation from the study will be recorded on the Case Report Form (CRF). Subjects who are randomized and subsequently withdraw informed consent, will not be replaced.
- 4. Those wishing to withdraw the study intervention should be aware that the intervention can be discontinued (i.e. no HBO treatments) without withdrawing from the trial and further data collection. Discontinuation of the study intervention itself does not constitute withdrawal from further participation in the study. After withdrawing from either the intervention or any further participation in the study, the participant's care should revert to standard care at the enrolling site. Consistent with OHRP and FDA guidance, participant data collected prior to withdrawal from the study is maintained in the study database, but no additional participant data will be collected from the participant or their medical record subsequent to withdrawal from the study.

7.3 SUBJECT TRACKING AND LOST TO FOLLOW-UP

To attain a high rate of follow up (>90%), the study team will request multiple phone numbers (home, cell phones, pagers, etc) and addresses from the subject and his/her relatives, friends, primary doctor (if available), clergy and clinics. At the time of consent or enrollment, proxy respondents will be asked to provide the address and telephone number of the place where the subject will likely reside following discharge. At the time of hospital discharge, each subject's disposition will be noted (nursing home, rehabilitation facility, another acute care hospital, subject's home, relative's home) so plans can be made for the Day 180 follow-up visit.

During the post discharge interval, a research coordinator will telephone subjects monthly for a health status inquiry and to maintain and update tracking information. During follow-up phone call, if medical

concerns are raised, subjects will be referred to their usual care provider if non-TBI related and to the trauma/TBI clinic if TBI related.

Subjects cannot be deemed "Lost to Follow" without the HOBIT Operations Committee approval. The site PI must present a case to the Operations committee that includes the efforts exerted to locate the study subject. The Site PI may be asked to continue their efforts prior to approval.

8 STUDY ASSESSMENTS AND PROCEDURES

8.1 EFFICACY ASSESSMENTS

Primary Outcome: The GOS-E will be performed at Day 30 (\pm 7 days), Day 90 (\pm 14 days), and Day 180 (\pm 21 days). The Day 30 and Day 90 assessments may be done by telephone interview, although in person interviews are preferred. Barring unusual circumstances, the subject should be interviewed in person rather than by telephone for the Day 180 GOS-E assessment. The GOS-E will be done by a trained and certified investigator who is either a nurse, physician, or neuropsychologist. The Day 30, 90 and 180 GOS-E must be done by a blinded assessor(s).

Secondary Outcomes: Intracranial pressure will be monitored and recorded during the treatment period. Brain tissue oxygen will be recorded at sites that utilize brain tissue PO2 monitoring.

8.2 CLINICAL DATA

Baseline Data

- a. Baseline data: The data collected during the baseline phase of the trial is used to validate eligibility for enrollment into the trial, including, but not limited to, the inclusion/exclusion criteria. Additionally, demographic information, labs, vital signs, medical history, and information related to the accident (e.g., mechanism of injury) are collected. If a subject is meets study inclusion/exclusion criteria but is not randomized, the reason is captured on the Screen Failure Log.
- b. Injury severity: The Abbreviated Injury Score (AIS), from which the Injury Severity Score (ISS) can be derived, will be collected to allow quantitative and consistent characterization of associated injuries.
- c. Baseline Head CT scans: Sites will read the baseline Head CT scans to ensure that a traumatic intracranial abnormality exists. Head CTs will be evaluated for monitor placement. Baseline CT scans will be sent to the HCMC (Central Reader) for review at a later time
- d. Data for International Mission for the Prognosis and Analysis of Clinical Trials in TBI (IMPACT) prognostic model: Specific data to predict 6-month outcome will be collected on admission.

These include: age, motor score, pupil reactivity.

Treatment (Randomization/Day 1 through Day 6/Hospital Discharge)

- a. Treatment: Data are collected to document all study treatments and monitoring of ICP, CPP, FiO2, brain tissue PO2, and Mean Arterial Pressure (MAP).
- b. Therapeutic intensity levels and GCS will be documented daily during the treatment period.
- c. Surgical Procedures: All surgical procedures performed until Day6 or Discharge (whichever occurs first) will be documented in the database.
- d. First follow up Head CT scan: The first follow up head CT scan will be sent to the HCMC (Central Reader) for review at a later time.
- e. Hospital discharge information will be collected including discharge location.

Follow-up assessments

The GOSE will be assessed at all follow-up visits (see primary efficacy outcome above)

8.3 SAFETY AND OTHER ASSESSMENTS

All adverse events (AEs) will be recorded through Day 6 or Discharge, whichever comes first. All serious adverse events (SAEs) will be recorded through the end of study.

- Blood pressure will be monitored via an arterial line during the treatment period and mean arterial pressure will be recorded (MAP) by the clinical team. Hypotension will be defined as MAP<70. The extent and duration of hypotension will be recorded.
- ICP will be monitored by the clinical team and the duration and extent of intracranial hypertension (ICP>22 mmHg) will be recorded.
- Cerebral perfusion pressure will be monitored by the clinical team. The extent and duration of cerebral hypoperfusion (CPP <60 mmHg) will be recorded.
- FiO2 levels will be monitored daily.
- Chest x-rays will be obtained as clinically indicated to assess for subcutaneous emphysema, pneumothorax, pneumonia, infiltrates suggestive of pulmonary oxygen toxicity/ARDS.

8.4 Adverse Events and Serious Adverse Events

8.4.1 DEFINITION OF ADVERSE EVENTS (AE)

An Adverse Event (AE) is any unfavorable and unintended sign (including an abnormal

laboratory finding), symptom, or disease temporally associated with the use of a medical treatment or procedure that may or may not be considered related to the medical treatment or procedure. An AE is a term that is a unique representation of a specific event used for medical documentation and scientific analyses.

8.4.2 DEFINITION OF SERIOUS ADVERSE EVENTS (SAE)

An adverse event (AE) or suspected adverse reaction is considered "serious" if, in the view of either the investigator or sponsor, it results in any of the following outcomes: death, a life-threatening adverse event, or prolongation of existing hospitalization, a persistent or significant incapacity or substantial disruption of the ability to conduct normal life functions. Important medical events may also be considered serious when they require medical or surgical intervention to prevent death, risk of permanent injury or disability, or prolonged hospitalization.

The population being studied has a high rate of clinically expected adverse events related to their underlying condition and standard treatment, independent of any research intervention. Subjects with severe TBI have an average of 3 critical complications per subject. This subpopulation of the most severely injured subjects has a mortality rate of 40%. Examples of common medical events in this population include (but are not limited to): ventilator associated pneumonia, venous thromboembolic disease, or progressive cerebral edema. Examples of common medical or surgical interventions include: evacuation of an intracerebral hematoma secondary to ventriculostomy insertion, or inferior caval filter placement to prevent pulmonary embolism.

Subjects may also incur AE that could be expected to occur at higher rates because of the study intervention with hyperbaric exposure. These include medical events such as exacerbated lung injury, oxygen related seizures, or interventions such as placement of a chest tube for a pneumothorax associated with an HBO treatment. Particular attention will be paid to potential complications from HBO treatment listed in section 9.4.

Pre-existing medical conditions or unchanged, chronic medical conditions. Pre-existing medical conditions or unchanged, chronic medical conditions are NOT considered AEs and should not be recorded on the AE case report form (CRF). These medical conditions should be adequately documented on the medical history and/or other source documents. In the HOBIT Trial, any medical condition not present prior to randomization but that emerge after randomization are considered AEs.

Exacerbation of Pre-existing medical conditions. A pre-existing medical condition judged by the investigator to have worsened in severity or frequency or changed in character is considered an adverse event.

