Endpoints:	Primary Endpoint . The primary analysis will use the intention to treat (ITT) sample to compare the proportion of favorable outcomes in the 6-month dichotomized, severity adjusted, GOS-E (section 11.1 of the SAP) in each treatment arm to control dose regimen. Favorable outcome for an individual subject is defined according to a sliding dichotomy (Murray, 2005), where the definition of favorable outcome varies according to baseline prognosis. Prognosis will be defined according to the probability of poor outcome predicted by the IMPACT Core Model (Steyerberg EW, 2008); see section 11.1.2.1 of the SAP). The favorable outcome definition				

me	 mary endpoint will analyze the GOS-E at 26 weeks; intermediate easurements will be taken at 4, 13 weeks. condary Endpoints: To analyze the level and duration of intracranial hypertension (> 22 mmHg) in hyperoxia-treated versus control groups. To analyze the therapeutic intensity level (TIL) scores for controlling intracranial pressure (ICP) in hyperoxia-treated subjects compared to controls. At sites utilizing brain tissue PO2 monitoring, analyze the level and duration of brain tissue hypoxia (brain tissue PO2 < 20 mmHg) in HBO-treated groups versus control (van den Brink 2000).
Sec	 To analyze the level and duration of intracranial hypertension (> 22 mmHg) in hyperoxia-treated versus control groups. To analyze the therapeutic intensity level (TIL) scores for controlling intracranial pressure (ICP) in hyperoxia-treated subjects compared to controls. At sites utilizing brain tissue PO2 monitoring, analyze the level and duration of brain tissue hypoxia (brain tissue PO2 < 20 mmHg) in
	 mmHg) in hyperoxia-treated versus control groups. 2. To analyze the therapeutic intensity level (TIL) scores for controlling intracranial pressure (ICP) in hyperoxia-treated subjects compared to controls. 3. At sites utilizing brain tissue PO2 monitoring, analyze the level and duration of brain tissue hypoxia (brain tissue PO2 < 20 mmHg) in
	 controlling intracranial pressure (ICP) in hyperoxia-treated subjects compared to controls. 3. At sites utilizing brain tissue PO2 monitoring, analyze the level and duration of brain tissue hypoxia (brain tissue PO2 < 20 mmHg) in
	duration of brain tissue hypoxia (brain tissue PO2 < 20 mmHg) in
	 To compare the type and rate of serious adverse events (SAEs) between hyperoxia treatment arms and control.

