8.4.4 TIME PERIOD AND FREQUENCY FOR EVENT ASSESSMENT AND FOLLOW-UP

The occurrence of an adverse event (AE) or serious adverse event (SAE) may come to the attention of study personnel during study visits and interviews of a study participant presenting for medical care, or upon review by a study monitor.

Certain adverse events will be captured and reported in WebDCU[™]. Information to be collected includes time of onset, clinician's assessment of severity, relatedness to study intervention, and time of resolution/stabilization of the event. All AEs occurring through Day 6 or Discharge, whichever comes first must be reported in WebDCU[™]. After Day 6 or Discharge, whichever comes first, only serious adverse events will be reported in WebDCUTM.All AEs will be followed to adequate resolution/stabilization or subject end of study.

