Critical hypotension (MAP<70 mmHg)	This AE is not specific to HBO therapy, but related to transfer from critical care unit (e.g. disconnecting and reconnecting of lines). It is expected to be the same in all groups but could demonstrate differences if the process of transferring to the dive chamber causes increased AEs. This should be analyzed as active vs. control.
Seizures during HBO treatment	These are expected to occur immediately proximal to treatment as a function of dose oxygen toxicity (rather than cumulative exposure). It is possible to have multiple episodes of AE. Subjects with a baseline propensity to seize may elevate the numerator for this AE.

Hypercarbia during transportation (PaCO2>45 mmHg)	This AE is not specific to HBO therapy, but related to transfer from critical care unit (e.g. disconnecting and reconnecting of lines). It is expected to be the same in all groups but could demonstrate differences if the process of transferring to the dive chamber causes increased AEs. This should be analyzed as active vs. control.
---	---

All AEs and SAEs are summarized by preferred term and associated system-organ class according to the MedDRA adverse reaction dictionary and by treatment group in terms of frequency of the event, number of subjects having the event, time relative to randomization, severity, and relatedness to the treatment. Cumulative incidences of the specific SAEs related to HBO, as well as all SAEs, will be compared across arms. Additional evaluation of safety events will be conducted adjusting for relative baseline co-variants, such as age at baseline and GCS score.

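### The SAE definition omits new hospital admission, so after discharge a readmission counts only if it meets another criterion, and otherwise goes unrecorded

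*Protocol*

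**What the plan says.** Four parts of the protocol bear on this.

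- **Definition (8.4.2).** An event is serious, in the view of the investigator or the sponsor, if it results in "death, a life-threatening adverse event, or prolongation of existing hospitalization, a persistent or significant incapacity", or if it substantially disrupts normal life functions. There is also a discretionary route: "Important medical events may also be considered serious when they require medical or surgical intervention to prevent death", or to prevent permanent injury, disability or a prolonged stay. No criterion names a new inpatient admission. The amendment history has no entry for 8.4.2, so this is the current text.
- **Recording windows (8.3 and 8.4.4).** For adverse events in general: "All adverse events (AEs) will be recorded through Day 6 or Discharge, whichever comes first". For serious ones: "All serious adverse events (SAEs) will be recorded through the end of study". Section 8.4.4 confirms the cut: "After Day 6 or Discharge, whichever comes first, only serious adverse events will be reported".
- **Use of the data (1.1 and 9.4).** A secondary endpoint is "To compare the type and rate of serious adverse events (SAEs) between hyperoxia treatment arms and control". The analysis section adds: "Cumulative incidences of the specific SAEs related to HBO, as well as all SAEs, will be compared across arms".
- **Related provisions.** Section 8.4.5 refers to the safety monitoring plan for reporting detail. Section 7.3 provides monthly telephone calls after discharge that ask about health status.

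**The concern.** From the earlier of Day 6 and discharge, the seriousness definition decides whether an event enters the database. A gap in the definition then becomes a gap in the data, not just a question of labelling.

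The hospitalization criterion works only while the subject is already in hospital. Once the subject has gone home or to a rehabilitation facility, an illness that sends the subject back does not meet it. If no other criterion applies, and no one uses the important-medical-event route, the event is neither an SAE nor a recordable adverse event.

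Three consequences follow for the comparison between arms:

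- The count of all SAEs over six months is incomplete in a way that depends on when each subject left hospital.
- The remaining route relies on judgement, in a trial where treatment is not blinded (6.3).
- Later review cannot repair the loss. The independent medical safety monitor and the DSMB review what has been reported (10.1.4), and an event never entered reaches neither.

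**Working it through.** No formula underlies this point and the protocol states no figure to reproduce. The check sets the definition against the recording windows.

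**Step 1. What applies in each period (8.3, 8.4.2, 8.4.4).**

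| Period | Non-serious events recorded? | Can the hospitalization criterion be met? |
|---|---|---|
| In hospital, up to Day 6 | Yes | Yes, if the stay is lengthened |
| In hospital, after Day 6 | No | Yes, if the stay is lengthened |
| After discharge, event causing a readmission | No | No: there is no current stay to lengthen |

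Only in the last row are both safeguards absent.

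**Step 2. One event in two settings.** Take a pneumonia that is not life-threatening, leaves no incapacity, does not substantially disrupt normal life functions, and is not designated an important medical event.

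- If it arises on Day 12 of the index stay and delays discharge, it is an SAE and is reported.
- If it arises after discharge and leads to a readmission, it meets no criterion and is not recorded.

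The clinical content is the same; only the place of onset differs. If an intervention changed length of stay, SAE rates could differ between arms through ascertainment alone. The protocol gives no evidence that this happens, so it is a possibility and not a demonstrated bias.

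**Step 3. Which comparisons are exposed.** Section 3 lists the SAEs of special interest as pneumothorax secondary to HBO, pulmonary dysfunction, pneumonia, and seizures during HBO. Section 9.4 expects pneumothorax during the dive, seizures close to treatment, and pulmonary dysfunction and pneumonia to worsen over successive dives.

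The length of the dive course follows from 6.1.2: at most 10 dives, hence 9 intervals. The first interval is at least 8 hours and the other 8 are 12 hours, plus or minus 2.

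- Shortest first interval, nominal spacing: 8 + 8 × 12 = 104 hours = 4.3 days.
- All nine intervals at 14 hours (for the first interval this is an assumption, since only its minimum is fixed): 9 × 14 = 126 hours = 5.25 days.

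The course therefore falls largely within the window in which every adverse event is recorded, unless the subject is discharged early. The exposed parts are the all-SAE comparison and late pneumonia or other pulmonary events.

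**Step 4. Can the loss be sized?** Counting missed events needs a readmission rate and the share of readmissions that meet no other criterion. The protocol gives neither, nor a typical discharge day. What can be computed is the share of the 180-day follow-up lying after an assumed discharge day d, which is (180 − d)/180:

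- d = 10: 170/180 = 94%
- d = 20: 160/180 = 89%
- d = 40: 140/180 = 78%
- d = 60: 120/180 = 67%

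These are shares of calendar time without a usable hospitalization criterion. They are not shares of events missed.

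**The case against.** A reader might infer three stronger claims, and the documents support none of them.

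- **That readmissions are never SAEs.** A readmission event still counts if it is fatal, life-threatening, incapacitating or substantially disruptive of normal life functions, or if it is designated an important medical event. Respiratory failure, for instance, would commonly qualify as life-threatening.
- **That the trial misses the harms it cares about most.** By the protocol's own account those cluster at or near the dives, and a seizure after discharge is not a seizure during HBO. Deaths are always SAEs and are analysed separately at 30 days, 3 months and 6 months (9.4).
- **That the calendar shares above measure the loss.** They do not, because events are not spread evenly over follow-up.

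Other objections carry some weight:

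- The safety monitoring plan is not available here and may hold a fuller definition. However, 8.4.5 cites it for reporting, while 8.4.2 is where the protocol fixes the definition. If the plan does include admissions, the two documents disagree and need reconciling.
- The odd placement of the conjunction in the definition suggests dropped words. Whether they were lost in drafting or in reading the file cannot be settled from the text. A loss in reading is speculation, and the sentence should be checked against the source file.
- Section 3 names pneumonia among the SAEs, which could be read as making it serious in itself. The protocol does not say so, and 8.4.2 sets the test by outcome.
- Collection routes exist: the AE form is available as optional at Days 30, 90 and 180 (1.3), and there are monthly calls. But the definition still decides what is entered.
- Seriousness may be judged by the sponsor as well as the investigator, which tempers the concern about unblinded judgement. It helps only if the event is brought to the sponsor's attention.

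**Conclusion.** The point holds in limited form. As written, a post-discharge readmission is not an SAE merely because the subject was admitted. Where no other criterion is met and the event is not judged an important medical event, nothing is recorded. The all-SAE comparison across arms is therefore incomplete for the period after discharge, and late pneumonia and pulmonary events are the named harms most likely to be affected. The dive-related harms are largely captured.

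The number of missed events, and whether the loss differs between arms, cannot be estimated from the protocol. The primary endpoint, the adaptive rules, the sample size and the error rates are unaffected. The conclusion assumes that 8.4.2 is applied as it stands and that no other trial document supplies an admission criterion. The correction is worth making because it is cheap and improves safety capture.

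**What to change.** - In 8.4.2, make the criterion inpatient hospitalization, covering both a new admission and the lengthening of a current stay. Except planned transfers to rehabilitation and elective admissions.
- Align the adverse event CRF and the safety monitoring plan with that wording.
- Add a direct question about hospital admissions since the last contact to the monthly calls in 7.3. The contact is already scheduled.

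The cost is a one-phrase protocol amendment with matching edits to the other documents, and a modest rise in the number of SAE reports for sites and the safety monitor to process.
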